7.2 Institutional Review Board (IRB) Review

The protocol will be submitted to the IRB for review and approval. Approval of the protocol must be obtained before initiating any research activity. Any change to the protocol or study team will require an approved IRB amendment before implementation.

A study closure report will be submitted to the IRB after all research activities have been completed.

Other study events (e.g. data breaches, protocol deviations) will be submitted per Yale IRB's policies.

7.3 Subject Confidentiality

Subject confidentiality is held in strict trust by the research team. Subject medical record review will be limited to the just the elements needed to complete the study. Only authorized HIPAA and GCP trained study team members will be allowed to extract research data from medical records and enter it into VOICES database. No direct subject identifiers will be entered into VOICES data analysis database.

Each subject will be assigned a unique study number. A master list linking the unique study number to the human subject will be maintained in a secure database file.

7.4 Deviations/Unanticipated Problems

If the study team becomes aware of an anticipated problem (e.g. data breach, protocol deviation), the event will be reported to the IRB by e-mail or via the IRES system as directed by the IRB.

7.5 Data Collection

Data of the study will be entered into a secure database on a secure server. In this study, the following materials will be collected from human subjects: questionnaire, study subject's study ID, and signature. All paper documents will be maintained in a locked file, separate from other clinical records to assure confidentiality. All electronically stored data will be encrypted and password-protected. Only the primary investigator, co-investigators, study coordinator and programmers will have access to subjects' data. All datasets will be de-identified and only known to study investigators involved in consent and data acquisition. All information relating to participating subjects will be deidentified.

7.6 Data Quality Assurance

The VOICES system will be designed to ensure compliance with good research practice regarding the management of research data containing Protected Health Information (PHI). VOICES will adopt comprehensive security strategies that will assure the confidentiality and privacy of the patient and clinical information. Only authorized users will have access to patient PHI, which will help assuage concerns participants may have regarding the privacy and security of their data. The guidelines contained in the Common Framework give a detailed specification of technical architecture, privacy safeguards, and several approaches to health information exchange. We will utilize this framework to protect patient privacy and keep PHI under strict local control. We will continuously evaluate our security practices in order to quickly identify any new vulnerabilities that could compromise VOICES integrity and privacy. We will utilize the Yale Information Technology Services (ITS) existing privacy and security practices and technology, and incorporate Yale ITS-consistent policies into VOICES development and implementation. In addition to tier separation and firewall protection, the three-tiered architecture maintains VOICES security, confidentiality, and privacy. VOICES will maintain data security with appropriate encryption, system controls and audit trails.

7.7 Study Records

Documents that will be considered study records for this study are consent forms, demographics and post-use surveys.

7.8 Access to Source

All documents will be collected electronically for the purpose of this study. All electronically stored data will be encrypted and password-protected. Only the primary investigator, co-investigators, study coordinator and programmers will have access to subjects' data. All datasets will be de-identified and only known to study investigators involved in consent and data acquisition.

7.9 Data or Specimen Storage/Security

Data will be collected and stored digitally, and maintained on a securely encrypted database server with password protection.

7.10 Retention of Records

Data will be retained based on Yale IRB policy.

7.11 Study Monitoring

The Principal Investigator (PI) will be responsible for ensuring participants' safety on a daily basis.

7.12 Data Safety Monitoring Plan

The DSMP will be monitored by the study team. The Principal Investigator (PI) will be responsible for ensuring participants' safety on a daily basis. To ensure that we are identifying both the adverse events that we might anticipate as well as those that we might not, the PI will review each case where either: (1) a report was made to PSE or (2) a patient was admitted to the hospital for safety to assess for any potential adverse events. The Data and Safety Monitoring Team (DSMT) will consist of Drs. [name], [name], and [name]; this team will monitor participant safety, evaluate the progress of the study, and review procedures for maintaining the confidentiality of data, the quality of data collection, management, and analyses. They will monitor the study for reports of any adverse or unexpected events. Study participants will be advised to contact the study team to report any adverse events or concerns. VOICES will only be administrated for the intervention group, and there will be no control groups. The PI and the investigative team will monitor data and safety at the monthly study team meetings.

The following will be reviewed:

- Cumulative accrual
- Enrollment of subjects who meet the study eligibility criteria only
- Recruitment is proceeding as planned
- The informed consent process is conducted appropriately; informed consent is obtained
- Evaluate the progress of the trial, including periodic assessments of data quality and timeliness, recruitment, accrual and retention, participant risk versus benefit, and other factors that can affect study outcome
- Consider factors external to the study when relevant information becomes available, such as scientific or therapeutic developments that may have an impact on the safety of the participants or the ethics of the trial
- Review study performance, make recommendations, and assist in the resolution of problems reported by the PI
- Evaluate data completeness and quality and as specified in the protocol

Prior to proceeding with any study procedures:

- Review the research protocol, informed consent documents and plans for data safety and monitoring
- Protect the safety of the study participants
- Ensure the confidentiality of the study data and the results of monitoring
- Review procedures for the privacy and confidentiality of subjects
- Review cumulative attrition and attrition by gender and race/ethnicity
- Review dropouts and ensure reason for withdrawal from the study are documented

The principal investigator will be responsible for monitoring the data, assuring protocol compliance, and conducting the safety reviews. During the review process the principal investigator will evaluate whether the study should continue unchanged, require modification/amendment, or close enrollment. The principal investigator and the

Institutional Review Board (IRB) and the NIA have the authority to stop or suspend the study or require modifications.

7.13 Study Modification

For any study modifications, we will update this study protocol. Then we will submit the updated protocol to Yale IRB for approval. Once approved the changes can be implemented in the study.

7.14 Study Discontinuation

N/A

7.15 Study Completion

The study will be completed by December 31th 2022. The PI will notify Yale IRB of the study completion.

7.16 Conflict of Interest Policy

The independence of this study from any actual or perceived influence, such as by the pharmaceutical industry, is critical. Therefore, any actual conflict of interest of persons who have a role in the design, conduct, analysis, publication, or any aspect of this trial will be disclosed and managed. Furthermore, persons who have a perceived conflict of interest will be required to have such conflicts managed in a way that is appropriate to their participation in the trial. The study leadership in conjunction with the appropriate conflict of interest review committee has established policies and procedures for all study group members to disclose all conflicts of interest and will establish a mechanism for the management of all reported dualities of interest.

All investigators will follow the applicable conflict of interest policies.

7.17 Funding Source

The study is funded by the Yale Claude D. Pepper Older Americans Independence Center OAIC Sponsor Award (IRES #: 18-001844-011).

7.18 Publication Plan

At the completion of this study and the feasibility study for older adults with cognitive impairment, we expect to enhance the VOICES tool and create all related and necessary user guides. We anticipate that if feasible, VOICES will inform development of national Elder Mistreatment (EM) intervention and screening guidelines on a generalizable scale that will broaden the base for EM identification and intervention while closing health disparity gaps and respecting the autonomy of older adults. Yale University is committed to open and timely dissemination of research outcomes and is aware of and agrees to abide by the principles for sharing research resources.

8 Appendices

Appendix #	Title	Section	Topic
------------	-------	---------	-------

9 List of Tables

7. ANALYTIC PLAN
 - 7.1. Analysis of Primary Outcome
 - 7.2. Analysis of Other Pre-Specified Outcome Measures

REFERENCES

STUDY SUMMARY (revised 5/16/2023)

Title	The Feasibility of the VOICES Digital Health Tool for Elder Mistreatment Screening in the Primary Care Setting
Study Design	The design is a single arm trial to develop the digital intervention and conduct a feasibility study across five important areas including: acceptability, demand, implementation, practicality, and limited efficacy.
Study Duration	7 months
Trial Sites	Yale Internal Medicine Associates (YIMA).
Objective	The primary objective of this study is to perform a feasibility evaluation of the VOICES screening tool among 80 older adults in primary care settings.
Number of Subjects	Over the course of this project, we recruited 80 participants.
Main Inclusion Criteria	
Inclusion Criteria:
 
 1. Age 60 or above 2. Living in Community Dwelling 3. Able to consent and communicate in English 4. Has no risk of COVID-19 5. Agrees and able to use the iPad 6. Stated willingness to comply with all study procedures and availability for the duration of the study 7. Provision of signed informed consent, or assent if LAR provides consent
Intervention	Our intervention is innovative because it utilizes best practices, and innovations in the design and development of digital health to create the one of its kind VOICES EM Intervention. As an easy-to-use, user-friendly EA intervention that runs on tablets with the information and messages displayed on the screen and spoken through headphones for privacy. VOICES delivers content specifically designed to target three factors (attitudes, subjective norms, perception of control) while providing accurate education on EM and APS response and dispelling myths and stereotypes surrounding victimization. VOICES will address perceptions of control making it easy to self-report and ask for help. Another innovative feature of VOICES is the ability to deliver health information through the use of digital tools, multimedia, and digitally guided interviews to older adults to increase awareness of EM.
Duration of Intervention	One session 8.8 minutes on average
Primary Outcome	The primary outcomes are participation and usage. Participation will be determined by the number of patients enrolled in VOICES. Usage will be determined by the number of patients enrolled in the study that complete the VOICES tool.
Primary Analysis	Primary outcomes will be tabulated as counts and frequencies.

Other Pre-Specified Outcome Measures	
 1. Acceptability 2. Demand 3. Practicality 4. Efficacy of the Brief Negotiation Interview 5. Efficacy of Self-Identification on Self-Disclosure 6. Accuracy
--------------------------------------	--

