6.1 Treatment – Device

6.1.1 Intended Use for Device (provide the following information for each device being investigated in the study)

The VOICES tool is intended to be used primarily to identify suspicion of elder mistreatment.

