6.3.2 Informed Consent

We will pay special attention to the ethical issues and the unique challenges of EM research as well as to consenting and enrolling older persons in our study. The consent process informs a volunteer about the study and fully explains the purpose of the research, that this is a research study, that participation is voluntary, and that the participant has the right to stop at any time. Our consent includes all of the eight basic elements of informed consent as articulated by 45 CFR §46.116, 21 CFR §50 and Yale IRB Policy 200 Informed Consent for Human Research) and the additional elements of informed consent. Before agreeing to participate in VOICES, potential subjects (and if needed their LAR) will be made aware of and understand the risks of participation. They are the following:

- A statement that the study involves research. This includes:
 - An explanation of the purposes of the research, stressing that this is not an intervention
 - The expected duration of the subject's participation
 - A description of the procedures to be followed
 - A description of any foreseeable risks or discomforts to the subject.
 - A description of any expected benefits to the subject or to others
 - When applicable, a disclosure of appropriate alternative
 - A statement explaining how confidentiality of data will be managed
 - An explanation of the risk of injury
 - List of whom to contact with questions about the research, research subjects' rights, or in the event of a research-related injury to the subject, that include: Principal Investigator's contact information and IRB Administrator's contact information
- A statement that:
 - Participation is voluntary
 - Refusal to participate will involve no penalty or loss of benefits to which the subject is otherwise entitled
 - The subject may discontinue participation at any time without penalty or loss of benefits to which the subject is otherwise entitled.
- In addition to the eight required elements of informed consent, additional elements are added to the consent. They include:
 - A statement that VOICES may involve risks to the subject which are currently unforeseeable;

- Anticipated circumstances in which the subject's participation may be terminated by the PI;
- Any additional costs to the subject that may result from participation in the research;
- The consequences of a subject's decision to withdraw from the research and procedures for orderly termination of participation by the subject;

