4. OUTCOMES

The primary and Other Pre-Specified Outcome Measures are summarized in Table 1.

Table 1. Primary and Other Pre-Specified Outcome Measures		
Domain	Measure (P,O)	Source and Frequency
Implementation	Participation. Participation will be determined by the ratio of participants who are successfully enrolled to the total number of eligible patients. (P)	Study enrollment records
	Usage. Usage will be determined by the number of consented participants enrolled in the study who used VOICES to completion (P)	VOICES tool completion records
Acceptability	Participant satisfaction measured using post-use satisfaction survey with two 5-point Likert response set scales, developed by the research team (O)	Self-report, once per participant
Demand	Measured by the % of the patients who self-identified with elder mistreatment and the % who receive the Brief Negotiation Interview (BNI) portion of VOICES.	Measured by VOICES tool, once per participant
Practicality	Average time to consent & orient participants to the tool (O)	RA measurement, once per participant
	Average time needed to complete VOICES (O)	RA measurement, once per participant
	Average time patients perceived time of VOICES	Self-report, once per participant
Efficacy of the Brief Negotiation Interview	Measured as % participants that change their self-identification response after completing the educational component (O)	Measured by VOICES tool, once per participant
Efficacy of Self-Identification on Self-Disclosure	Measured as % of patients who disclose among those who self-identified (O)	Measured by VOICES tool, once per participant
Accuracy	Measured as percent of classified EM cases that were positive based on social worker assessment, and those referred to Adult Protective Services (APS). (O)	Measured by the outcome of the social worker assessment and by the outcome APS evaluation.

EM: Elder Mistreatment; BNI: Brief Negotiation Interview; APS: Adult Protective Services

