4.2 Other Pre-Specified Outcomes

Acceptability: Participant satisfaction will be measured along multiple dimensions using post-use satisfaction survey with two 5-point Likert response set scales, developed by the research team. Scale 1: Likert scale 1-5, where 1= Very Dissatisfied, and 5= Very Satisfied Scale 2: Likert scale 1-5, where 1= Strongly Disagree, and 5= Strongly Agree

Demand: Demand will be assessed through examining how likely will VOICES be used by patients. To do this, the size of target population of EM victims in the ED will be measured by the % of the patients who self-identified with elder mistreatment and the % who receive the Brief Negotiation Interview (BNI) portion of VOICES.

Practicality: Practicality will be assessed by observing the ease of VOICES use by patients. To do this, a series of steps will be watched to determine the efficiency of implementation measured by the average time (1) to consent & orient participants to the tool and (2) needed to complete VOICES documented by the Research Assistant; and (3) patients perceived time of VOICES as measured on post-survey. Each of these will be reported as part of the overall outcome.

Efficacy of the Brief Negotiation Interview: We will look at how many patients changed their readiness to identify and readiness to disclose after completing the Brief Negotiation Interview (BNI).

Efficacy of Self-Identification on Self-Disclosure: We will explore whether self-identification impacts likelihood of self-disclosure. Effect-size estimation measured by change in the % of patients who disclose among those who self-identified.

Accuracy: To understand the accuracy of the VOICES tool, a preliminary evaluation of the accuracy of VOICES as a screening tool in correctly classifying EM cases that were positive based on social worker assessment, and those referred to Adult Protective Services (APS). The percent correct classification will be reported.

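### Protocol 6.3.2 requires consent to stress that the research involves no intervention, which conflicts with the protocol's own wording and with the SAP's description and outcomes

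*SAP*

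**What the plan says.** **Consent.** Protocol 6.3.2 itemises what the consent process must cover. The item on the study's purpose reads: "An explanation of the purposes of the research, stressing that this is not an intervention".

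**Protocol, elsewhere.**
- 6.1.1 gives the intended use: "The VOICES tool is intended to be used primarily to identify suspicion of elder mistreatment".
- 2.1.2 and 2.2 give the tool three functions: screening, educating and motivating.
- 6.2.3 makes relatedness to the intervention one of the criteria for a reportable adverse event.
- 7.12 states: "VOICES will only be administrated for the intervention group, and there will be no control groups".

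**SAP.**
- The Study Summary design row reads: "The design is a single arm trial to develop the digital intervention and conduct a feasibility study across five important areas". Limited efficacy is one of those areas.
- The summary's Intervention row says that the project set out to "create the one of its kind VOICES EM Intervention", and that "VOICES delivers content specifically designed to target three factors (attitudes, subjective norms, perception of control".
- Section 4.2, on efficacy of the Brief Negotiation Interview (BNI), reads: "We will look at how many patients changed their readiness to identify and readiness to disclose after completing the Brief Negotiation Interview (BNI". Section 7.2 repeats this and reports counts.
- Table 1 defines the same outcome as: "Measured as % participants that change their self-identification response after completing the educational component (O".

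The BNI is not named anywhere in the protocol.

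**The concern.** A person deciding whether to take part should be able to learn that the tool is built to influence whether they come to see themselves as mistreated and whether they say so. The one consent element that speaks to the nature of the research points the other way, and 6.3.2 asks for it to be stressed.

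This is more than a matter of labels. Under 3.2.1 and 6.3.5, a positive screen or a wish to self-report leads the research assistant to notify the care team, and a report to protective services may follow. Section 3.2.1 lists retaliation, loss of a caregiver and facility placement among the possible consequences of identification. The change that the SAP counts under efficacy is thus a step towards the protocol's own listed risks.

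**Working it through.** The point rests on comparing texts; no figure in the plan bears on it. The SAP's precision statements were checked for completeness. At N=80 the exact (Clopper-Pearson) 95% interval at 40/80 has width 0.2279, against 0.228 stated. The half-width for a mean is 1.96/√80 = 0.219 SD, or 0.223 SD with the t quantile, against 22% stated. Both reproduce, and neither enters the argument.

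1. **Scope of the clause.** In 6.3.2 it qualifies the purpose of the research and has no limiting word such as *medical*. Read literally, it denies any intervention.

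2. **Against the rest of the protocol.** A causality criterion tied to the intervention (6.2.3) and an intervention group that receives VOICES (7.12) cannot both stand beside a literal denial. Nor does the denial fit a tool described as educating and motivating (2.1.2, 2.2), or stronger support for self-disclosure as a potential benefit (3.2.2).

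3. **Against the SAP.** The tool is called an intervention, its content is aimed at attitudes, norms and perceived control, and change after that content is measured. Section 4.2 measures it as readiness after the BNI. Table 1 measures it as the self-identification response after the educational component. Both are changes following VOICES content.

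4. **How many outcomes.** Two of the six other pre-specified outcomes carry an efficacy label. Only the BNI outcome directly measures change after VOICES content. The second has self-identification as its named exposure, although 7.2 counts participants who change their willingness to disclose. Protocol 5.2 lists no efficacy or behaviour-change outcome.

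5. **The narrower meaning.** Section 3.2.1 says the study has no medical interventions. The capacity check in 6.1.2 and the comprehension questions in 6.3.2 and 6.3.5 say participation is not medical treatment. This makes the narrower meaning plausible, but the consent element itself does not say it.

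6. **What consent already covers.** Section 3.2.1 requires participants to be told that identification may lead to adverse events, and that identified mistreatment is reported to the care team. Section 6.3.2 requires procedures, risks and benefits to be described. None of these elements expressly requires saying that the tool aims to influence self-identification and disclosure, or that this change is measured.

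7. **Timing.** The protocol is dated 01/20/2022. The SAP summary was revised on 5/16/2023 and reports 80 participants as already recruited.

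**The case against.** The strongest reply is that the clause is shorthand for *not medical treatment*. The 6.3.2 comprehension question pairs voluntary participation with not being part of medical treatment. The list of consent elements has a matching voluntariness item, and its only apparent counterpart to the second half is the no-intervention clause. On that reading the two say the same thing, and the defect is loose wording. This stands as a plausible account of intent. It does not rescue the text, because an unqualified denial is what the protocol instructs staff to stress.

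It can also be said that the main risks are handled elsewhere in consent. That is correct, and it limits the point considerably: what remains uncovered is the tool's aim, not the consequences of disclosure.

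Two stronger readings are tempting, and the documents support neither.
- A reader might infer that all 80 participants were misinformed. The consent form is not in the reviewed text, and 6.3.2 is a list of elements, not the words participants saw. The description of procedures may have explained the educational content.
- A reader might infer that the study presents responses to persuasion as screening results. The protocol states the motivating function openly (2.1.2, 2.2, 3.2.2) and names no identification or disclosure rate as an outcome in 5.2. The SAP reports change after the educational content as an outcome of its own.

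**Conclusion.** The concern holds as a wrong required consent element. The clause in 6.3.2 conflicts with protocol 2.1.2, 2.2, 6.2.3 and 7.12, and with the SAP Study Summary, Table 1, 4.2 and 7.2. The protocol's omission of the BNI leaves the component whose efficacy is reported undescribed in the document that governs consent.

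Its reach is every participant to whom the element applied, 80 by the SAP's count. The share who receive the BNI is not stated. The conclusion assumes only that the consent process was meant to follow 6.3.2 as written; whether any participant was misled cannot be judged from these documents. Participation, usage, sample size and the primary analysis are unaffected. The correction is worth making because it concerns participant protection and costs little.

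**What to change.** - **Protocol 6.3.2:** replace the no-intervention clause with a statement that participation is not medical treatment. Add that VOICES includes education and a Brief Negotiation Interview intended to influence whether a person self-identifies and discloses, and that this change is measured.
- **Protocol 6.1.1 and 6.1.2:** name the BNI, so that the intended-use and administration sections match the SAP.
- **Consent already given:** new wording cannot alter it. Check the form actually used against this point and record the result.
- **Report:** describe VOICES as an educational and motivational intervention.
- **Planned pilot (protocol 5.1):** carry the corrected wording into its protocol and consent form.
- **SAP outcomes:** keep both efficacy outcomes. Removing pre-specified outcomes after recruitment to settle a wording conflict would invite a charge of selective reporting.

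The cost is one wording amendment through the IRB and a check of one form. No data collection or analysis changes.
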